1.0 Objectives

1.1 Describe the purpose, specific aims, or objectives.

Response: The primary objective of this study is to compare measures of ankle stability from an investigational weight bearing cone beam computed tomography (CT) scanner to the same measures on gravity stress X-ray in patients who have supination-external rotation ankle fractures.

The secondary objective is to assess inter-rater reliability of ankle stability measures from the investigational cone beam CT scanner and gravity stress X-ray between 2 independent radiologists.

An exploratory objective of this study is to determine if sensitivity of the investigational cone beam CT scan can be verified using the gravity stress X-ray as the gold standard.

1.2 State the hypotheses to be tested.

Response: The primary hypothesis is that the mean medial clear space will be different for the investigational weight bearing cone beam CT scan versus the gravity stress X-ray.

2.0 Background

2.1 Describe the relevant prior experience and gaps in current knowledge.

Response: Supination-external rotation (SER) or Weber B type ankle fractures are considered the most common type of ankle fracture¹⁻⁴. An SER fracture is considered unstable when it is associated with deltoid ligament rupture. Clinical findings of medial tenderness, swelling, and ecchymosis were once thought to be reliable for correctly determining the stability of SER ankle fractures, but have since proven to be poor predictors of deltoid ligament disruption^{3, 5}. Rupture of the deltoid ligament allows lateral talar shift, and can be identified by widening of the medial clear space on standard radiographs as well as stress radiographs^{6, 7}.

2.2 Describe any relevant preliminary data.

Response: Many studies have shown that gravity stress radiographs are necessary and are currently considered to be the gold standard for diagnosis of SER fractures⁵. Of all the methods that have been used to diagnose instability and investigate deltoid ligament integrity (clinical examination, weight bearing radiographs, stress radiography, magnetic resonance imaging (MRI), arthroscopy, ultrasound), none have been shown to be cost-effective, rapid, reliable, and easy to use⁴. Gravity stress

PROTOCOL TITLE: Comparison of a novel weight bearing cone beam computed tomography (CT) scan to gravity stress X-ray for determining instability of supination-external rotation type ankle fractures

radiographs are performed without a uniform method, are known to lack sensitivity, and are very user dependent. Therefore, more research is needed to determine which method is most accurate and efficient for SER fracture diagnosis.

2.3 Provide the scientific or scholarly background for, rationale for, and significance of the research based on the existing literature and how will it add to existing knowledge.

Response: Weight bearing on the extremity is thought to be more representative of the normal use of the ankle joint, and CT scan is known to deliver excellent bone detail for interpretation of images. The ability of weight bearing cone beam CT scanning to measure medial clear space may present a new opportunity to evaluate instability of SER ankle fractures.

2.4 Include complete specific citations/references.

Response:

3.0 Inclusion and Exclusion Criteria

3.1 *Describe the criteria that define who will be included or excluded in your final study sample.*

Inclusion: Subjects will be recruited from the clinical practices of the study investigators and will:

- have an isolated fibula fracture
- have medial clear space measuring less than 5 mm with clinical suspicion of instability and would normally require a gravity stress x-ray
- be willing and able to provide written informed consent
- be 18 or more years of age

Exclusion: Subjects will be excluded from study participation if they:

- are pregnant at the time of screening
- are prisoners
- have an open fracture
- have clinical signs of ankle deformity
- have had any type of previous ankle trauma or surgery on the affected foot
- have significant osteoarthritis or pre-existing ligamentous instability or pain in the affected ankle
- have an inability to stand in the weight bearing position during the CT scan

3.2 *Describe how individuals will be screened for eligibility.*

Response: Patients will be screened (see **Eligibility Form Attachment A** that will be used for screening purposes) and recruited by the research team in the Emergency Department or clinical offices of the investigators. Patient history will be obtained and physical examination will be performed, and standard X-rays will be obtained. When the medial clear space is less than 5 mm with clinical suspicion of ankle instability, patients are referred for a routine gravity stress X-ray.

3.3 *Indicate specifically whether you will include or exclude each of the following special populations: (You may not include members of these populations as subjects in your research unless you indicate this in your inclusion criteria.)*

PROTOCOL TITLE: Comparison of a novel weight bearing cone beam computed tomography (CT) scan to gravity stress X-ray for determining instability of supination-external rotation type ankle fractures

- *Adults unable to consent*
- *Individuals who are not yet adults (infants, children, teenagers)*
- *Pregnant women*
- *Prisoners*

Response: Adults unable to consent, individuals who are not yet adults, pregnant women, and prisoners will be excluded from this study.

3.4 *Indicate whether you will include non-English speaking individuals. Provide justification if you will exclude non-English speaking individuals.*

(In order to meet one of the primary ethical principles of equitable selection of subjects, non-English speaking individuals may not be routinely excluded from research. In cases where the research is of therapeutic intent or is designed to investigate areas that would necessarily require certain populations who may not speak English, the researcher is required to make efforts to recruit and include non-English speaking individuals. However, there are studies in which it would be reasonable to limit subjects to those who speak English: e.g., pilot studies, small unfunded studies with validated instruments not available in other languages, numerous questionnaires, and some non-therapeutic studies which offer no direct benefit.)

Response: Non-English speaking subjects will be included in this study. Based on previous experience, we expect that most if not all of our potential study subjects will be English-speaking. However, if we encounter a non-English speaking subject we will find someone who can orally translate (i.e., fluently speaks the same language as the subject, such as a family member) the study description and consent form to the subject.

4.0 Study-Wide Number of Subjects (Multisite/Multicenter Only)

4.1 *If this is a multicenter study, indicate the total number of subjects to be accrued across all sites.*

Response: This is not a multisite/multicenter trial.

5.0 Study-Wide Recruitment Methods (Multisite/Multicenter Only)

If this is a multicenter study and subjects will be recruited by methods not under the control of the local site (e.g., call centers, national advertisements) describe those methods. Local recruitment methods are described later in the protocol.

5.1 *Describe when, where, and how potential subjects will be recruited.*

PROTOCOL TITLE: Comparison of a novel weight bearing cone beam computed tomography (CT) scan to gravity stress X-ray for determining instability of supination-external rotation type ankle fractures

Response: Not applicable, this is not a multi-site study.

5.2 *Describe the methods that will be used to identify potential subjects.*

Response: Not applicable, this is not a multi-site study.

5.3 *Describe materials that will be used to recruit subjects. (Attach copies of these documents with the application. For advertisements, attach the final copy of printed advertisements. When advertisements are taped for broadcast, attach the final audio/video tape. You may submit the wording of the advertisement prior to taping to preclude re-taping because of inappropriate wording, provided the IRB reviews the final audio/video tape.)*

Response: Not applicable, this is not a multi-site study.

6.0 Multi-Site Research (Multisite/Multicenter Only)

6.1 *If this is a multi-site study where you are the lead investigator, describe the processes to ensure communication among sites, such as:*

- *All sites have the most current version of the protocol, consent document, and HIPAA authorization.*
- *All required approvals have been obtained at each site (including approval by the site's IRB of record).*
- *All modifications have been communicated to sites, and approved (including approval by the site's IRB of record) before the modification is implemented.*
- *All engaged participating sites will safeguard data as required by local information security policies.*
- *All local site investigators conduct the study appropriately.*
- *All non-compliance with the study protocol or applicable requirements will reported in accordance with local policy.*

Response: Not applicable, this is not a multi-site study.

6.2 *Describe the method for communicating to engaged participating sites:*

- *Problems.*
- *Interim results.*
- *The closure of a study*

Response: Not applicable, this is not a multi-site study.

7.0 Study Timelines

7.1 *Describe the duration of an individual subject's participation in the study.*

PROTOCOL TITLE: Comparison of a novel weight bearing cone beam computed tomography (CT) scan to gravity stress X-ray for determining instability of supination-external rotation type ankle fractures

Response: The subject will be enrolled in the study once informed consent is obtained. The study will conclude once they have had a gravity stress X-ray as standard of care, and a CBCT scan with the investigational weight bearing cone beam scanner.

7.2 Describe the duration anticipated to enroll all study subjects.

Response: It is anticipated that it will take 8 months to 1 year (based on analysis of the past frequency of patients with the diagnosis of an unstable SER fracture and the difficult nature of enrolling study patients) to enroll all study subjects.

7.3 Describe the estimated date for the investigators to complete this study (complete primary analyses)

Response: The estimated date for the investigators to complete the primary analysis is the first quarter of 2017.

8.0 Study Endpoints

8.1 Describe the primary and secondary study endpoints.

Response: The primary endpoint is after enrollment of 20 subjects estimated to provide significance by power analysis.

8.2 Describe any primary or secondary safety endpoints.

Response: The primary safety endpoint is the presence of any adverse event.

9.0 Procedures Involved

9.1 Describe and explain the study design.

Response: This study is a cross-sectional study designed to compare measures of stability from a gravity stress X-ray to the same measures on an investigational cone beam CT scanner.

9.2 Provide a description of all research procedures being performed and when they are performed, including procedures being performed to monitor subjects for safety or minimize risks.

Response: **Screening/Enrollment Visit:** If a patient presents with a potentially unstable SER type ankle fracture the subject's physician will screen them, in the emergency room or physician's office, to determine if they are eligible for the study (see attached **Eligibility Form, Attachment A**).

The determination of a potentially unstable SER type ankle fracture is made via a standard X-ray showing medial clear space less than 5 mm with clinical suspicion of instability. This criteria substantiates the potential diagnosis of an unstable SER ankle fracture with need for

PROTOCOL TITLE: Comparison of a novel weight bearing cone beam computed tomography (CT) scan to gravity stress X-ray for determining instability of supination-external rotation type ankle fractures

radiographic evaluation by a gravity stress X-ray. To confirm their diagnosis and for surgical treatment planning, patients are sent for a gravity stress X-ray as part of their standard of care.

The study will be explained to eligible subjects, and informed consent to participate in the study will be obtained at the time the subject is thought to have an unstable SER type ankle fracture (in the emergency room or physician's office). For females of childbearing age who consent to be in the study, a urine pregnancy test will be done in the emergency department or physician's office to confirm that the patient is not pregnant. Pregnant females will be excluded from the study (see attached **Eligibility Form, Attachment A**).

Study Visit: The subject will undergo a weight bearing CBCT scan of their affected ankle with the investigational portable cone beam CT scanner. This will be done at the same time or within 7 days as the gravity stress X-ray that is part of the routine clinical work-up for this injury. The scan with the investigational CBCT scanner is estimated to last approximately 25 seconds. The patient will be weight-bearing during the scan and can hold on to the built-in handles of the scanner for stability during the scan. The subject will be shielded from radiation to the thyroid and genitals with commercially available shields. The risks involved with this study include the risk of additional exposure to radiation delivered by the investigational CT scan. The investigational CBCT scanner exposes the patient to approximately 50% less radiation per scan than a conventional CT scanner. (Carrino et al 2014) With the investigational CBCT scan, there is the risk of pain caused by the need for weight bearing and/or flexion of an injured ankle. If for any reason the subject experiences undue discomfort the study will be stopped and the patient will be excluded from the study if the scan cannot be performed.

The patient will also fill out a visual analogue pain scale after both the investigational CT scan and gravity stress X-ray (**Attachment D**).

Reference: Carrino, J.A., et al., Dedicated cone-beam CT system for extremity imaging. *Radiology*, 2014. 270(3): p. 816-824.

9.3 Describe procedures performed to lessen the probability or magnitude of risks.

Response: The risks involved in inclusion in the study include the risk of additional exposure to radiation from the investigational CT scan. The investigational cone beam CT scanner exposes the patient to approximately 50% less radiation per scan than a conventional CT scanner. (Carrino et al 2014) The investigational scanner will be shielded per manufacturer specifications (see attachment B). The subject will be

PROTOCOL TITLE: Comparison of a novel weight bearing cone beam computed tomography (CT) scan to gravity stress X-ray for determining instability of supination-external rotation type ankle fractures

shielded from radiation to the thyroid and genitals with commercially available shields. To address the risk of pain caused by the need for weight bearing on the injured ankle, the scans will only last about 25 seconds. The subject will be provided with assistance entering and exiting the scanner, and the handles attached to the housing of the scanner can be held by the subject for balance (but not for substantial unloading of weight bearing) on the extremity to prevent falling.

Reference: Carrino, J.A., et al., Dedicated cone-beam CT system for extremity imaging. *Radiology*, 2014. 270(3): p. 816-824.

9.4 *Describe all drugs and devices used in the research and the purpose of their use, and their regulatory approval status.*

Response: This study involves the use of an investigational portable weight bearing 3D cone beam CT scanner produced by Carestream Health, Inc. Supporting evidence contends that the prototype is a non-significant risk device (see **Attachment C**).

9.5 *Describe the source records that will be used to collect data about subjects. (Attach all surveys, scripts, and data collection forms.)*

Response: Data will be collected from the patient's medical records for screening potential research subjects (see attached **Eligibility Form, Attachment A**). Demographic, X-ray and CT data, and a visual analogue pain scale score will be documented by the research coordinator, surgeon and radiologist (see attached **Data Collection Forms, Attachment D**).

9.6 *What data will be collected including long-term follow-up.*

Response: Demographic data (age, gender, race, height, weight), data from the gravity stress X-rays and CT scans (medial clear space distance, superior clear space distance, lateral overlap distance, lateral clear space distance, and lateral talar shift) and pain VAS data will be collected (**Attachment D**). The measures will be obtained by two independent radiologists. Additionally, a visual analogue pain score will be obtained from the patient after both the investigational CT scan and gravity stress X-ray. The actual amount of weight borne by the patient at the time of the CT scan will be measured by a scale embedded in the device.

9.7 *For HUD uses provide a description of the device, a summary of how you propose to use the device, including a description of any screening procedures, the HUD procedure, and any patient follow-up visits, tests or procedures.*

Response: Not applicable, this study does not involve a HUD device.

10.0 Data and Specimen Banking

PROTOCOL TITLE: Comparison of a novel weight bearing cone beam computed tomography (CT) scan to gravity stress X-ray for determining instability of supination-external rotation type ankle fractures

10.1 If data or specimens will be banked for future use, describe where the data/specimens will be stored, how long they will be stored, how the data/specimens will be accessed, and who will have access to the data/specimens.

Response: The images obtained from the investigational cone beam CT scan will be saved for future use. The images will be de-identified and saved in the PACS system at the Erie County Medical Center. The study investigators and Carestream Health, Inc. will have access to these files.

10.2 List the data to be stored or associated with each specimen.

Response: The images obtained from the investigational cone beam CT scans will be saved for future use.

10.3 Describe the procedures to release data or specimens, including: the process to request a release, approvals required for release, who can obtain data or specimens, and the data to be provided with specimens.

Response: Requests for data will be accepted verbally or in writing. The principal investigator will approve all requests for data. Only the study investigators and Carestream Health, Inc. will be granted access to the data. The images will be de-identified before they are released. Carestream Health, Inc. will be requesting de-identified images, from the study-related cone beam CT scans only, for promotion & marketing purposes, and to refine the methodology of the scanner.

11.0 Data Management

11.1 Describe the data analysis plan, including any statistical procedures.

Response: To test for a difference in medial clear space between gravity stress X-ray and weight bearing cone beam CT, we will use a paired t-test. Intraclass correlation coefficients (ICC) and corresponding 95% confidence intervals will be computed as a measure of inter-rater reliability for the two radiologists who will assess the medial clear space. Bland-Altman plots will be used to visually assess agreement.

We will also conduct receiver operating characteristic (ROC) curve analysis and report the area under the curve (AUC) and corresponding 95% confidence interval. Using medial clear space >4mm for the gravity stress X-ray as the gold standard, we will determine the optimal cut-point for the cone beam CT scan.

11.2 Provide a power analysis.

Response: Sample size calculation was based on paired t-test. Estimates from the literature suggest the standard deviation of the difference of

PROTOCOL TITLE: Comparison of a novel weight bearing cone beam computed tomography (CT) scan to gravity stress X-ray for determining instability of supination-external rotation type ankle fractures

medial clear space is around 1.5 mm. For a sample size of 20 patients and at the 0.05 significance level, we can obtain 80% power to detect a difference of at least 1mm.

11.3 Describe the steps that will be taken secure the data (e.g., training, authorization of access, password protection, encryption, physical controls, certificates of confidentiality, and separation of identifiers and data) during storage, use, and transmission.

Response: Data collection will be conducted by trained study personnel who have completed IRB training. Data (i.e., demographics and CT and X-ray measures) will be entered into an Excel spreadsheet. The images will be de-identified and saved electronically in the PACS system at Erie County Medical Center. Data will be password protected and subject identity will be coded to ensure confidentiality of information. Patient names will not be stored with the images and patient data, instead each subject will be assigned an ID number. A separate password-protected spreadsheet will contain subject names and ID numbers to link the two together. The PI will assume primary responsibility for the ongoing monitoring of the data and safety of the study. Consent forms and other identifiable information will be stored in locked files separately from the study data. All data will be stored in password protected files in the research office at UBMD Orthopaedics Location 2 at ECMC.

11.4 Describe any procedures that will be used for quality control of collected data.

Response: Data will be entered and verified at 100%. We will utilize the services of the UB Clinical Research Office (CRO) for routine study monitoring activity. The UB CRO monitor will source verify the data, including consent process, following first subject enrollment. Subsequent monitoring activities will be arranged with the CRO depending on subject enrollment. The images from the gravity stress X-ray and investigational CT scan will be provided to the participating radiologist in a blinded and random fashion. When all subjects have been enrolled and undergone their scans, the scans will be presented randomly without any identifying information, on two separate occasions for measurement. The average of the two sets of measurements will be used for primary analysis.

11.5 Describe how data and specimens will be handled study-wide:

Response: Screening data will be collected on forms by the surgeon, research coordinator and other trained study staff. Demographic data will be documented on forms by the research coordinator or assistant. Data from the CT scan and X-ray will be documented on forms by the radiologist. The images will be de-identified and saved on the PACS system at ECMC. All data and collections forms (see **Attachments A & D**) will be collected by the research coordinator and stored securely.

PROTOCOL TITLE: Comparison of a novel weight bearing cone beam computed tomography (CT) scan to gravity stress X-ray for determining instability of supination-external rotation type ankle fractures

11.6 What information will be included in that data or associated with the specimens?

Response: The following data will be collected: medical history, demographics, VAS pain score, and X-ray and investigational cone beam CT data (see **Attachment D**).

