Attachment A. Eligibility Form

SER Ankle Fracture Instability STUDY

ELIGIBILITY QUESTIONS

TODAY'S DATE: _____

PATIENT'S NAME: _____

Please answer the following questions for ALL patients diagnosed with a suspected unstable supination-external rotation type ankle fracture requiring a gravity stress X-ray. Please refer to the Inclusion Criteria column to determine if the patient is eligible.

Question	Answer	Inclusion Criteria
1.) Does the patient have a diagnosis of a potentially unstable SER type (Weber B) ankle fracture?	YES / NO	The patient's X-ray must show medial clear space less than 5 mm with clinical suspicion of instability
2.) Is the patient able to provide written informed consent?	YES / NO	Patients must be able to provide written informed consent.
3.) Is the currently imprisoned?	YES / NO	Patients must not be in prison.
4.) How old is the patient?	Age = _____	Patients must be at least 18 years-old.
5.) Did the patient have an open fracture?	YES / NO	Patients must NOT have an open fracture.
6.) Does the patient have clinical signs of ankle deformity?	YES / NO	Patient must NOT have clinical signs of ankle deformity.
7.) Did the patient have any type of previous ankle trauma or surgery on the affected ankle?	YES / NO	Patient must NOT have had any type of previous ankle trauma or surgery on the affected ankle.
8.) Does the patient have significant osteoarthritis or pre-existing ligamentous instability or pain in the affected ankle?	YES / NO	Patient must NOT have significant osteoarthritis or pre-existing ligamentous instability or pain in the affected ankle.

PROTOCOL TITLE: Comparison of a novel weight bearing cone beam computed tomography (CT) scan to gravity stress X-ray for determining instability of supination-external rotation type ankle fractures

10.) Is the patient pregnant?	Patient Verbal Response: YES / NO Urine pregnancy test result (for females who consent ONLY): Positive / Negative	The patient must NOT be pregnant. Females who consent to participate MUST have a negative urine pregnancy test.
11.) Can the patient stand in the weight bearing position?	YES / NO	The patient MUST be able to stand in the weight bearing position for the cone beam CT scan.
IS PATIENT ELIGIBLE FOR THE STUDY? YES / NO		
DID THE PATIENT CHOOSE TO ENROLL IN THE STUDY? YES / NO		
NOTES:		

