Attachment D: Data Form

SER Ankle Fracture Instability STUDY: DEMOGRAPHIC DATA COLLECTION FORM

STUDY ID#: _____

TODAY'S DATE: _____

AGE: _____

GENDER (check one): _____ Male

_____ Female

RACE: _____

HEIGHT: _____

WEIGHT: _____

PATIENT'S DOCTOR: _____

AFFECTED SIDE: _____ Right

_____ Left

COURSE OF TREATMENT: _____

PROTOCOL TITLE: Comparison of a novel weight bearing cone beam computed tomography (CT) scan to gravity stress X-ray for determining instability of supination-external rotation type ankle fractures

SER Ankle Fracture Instability STUDY: CT DATA COLLECTION FORM

STUDY ID #: _____

DATE OF CT SCAN: _____

RADIOLOGIST: _____

RESULTS OF CT SCAN:

Date of Measurement: _____

Medial Clear Space Distance: _____

Superior Clear Space Distance: _____

Lateral Overlap Distance: _____

Lateral Clear Space Distance: _____

Lateral Talar Shift: _____

Total Weight Bearing: _____

Percent Weight Bearing: _____

PROTOCOL TITLE: Comparison of a novel weight bearing cone beam computed tomography (CT) scan to gravity stress X-ray for determining instability of supination-external rotation type ankle fractures

SER Ankle Fracture Instability STUDY: X-RAY DATA COLLECTION FORM

STUDY ID #: _____

DATE OF X-RAY: _____

RADIOLOGIST: _____

RESULTS OF X-RAY:

Date of Measurement: _____

Medial Clear Space Distance: _____

Superior Clear Space Distance: _____

Lateral Overlap Distance: _____

Lateral Clear Space Distance: _____

Lateral Talar Shift: _____

PROTOCOL TITLE: Comparison of a novel weight bearing cone beam computed tomography (CT) scan to gravity stress X-ray for determining instability of supination-external rotation type ankle fractures

Visual Analogue Scale

On a scale of 0 to 10, where 0 equals no pain and 10 equals extreme pain, please circle the number that best represents how much ankle pain you experienced during the scan.

| | | | | | | | | | |
0 1 2 3 4 5 6 7 8 9 10

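### Does admitting ankles already 4 to 5 mm wide at rest spoil the exploratory ROC analysis, whose reference is a stress film above 4 mm?

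*Combined protocol and SAP*

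**What the plan says.** **Entry.** Section 3.1 requires patients to "have medial clear space measuring less than 5 mm with clinical suspicion of instability". Section 3.2 says that at screening "standard X-rays will be obtained", and section 9.2 places the limit on that film: "standard X-ray showing medial clear space less than 5 mm with clinical suspicion of instability". Attachment A repeats that the film "must show medial clear space less than 5 mm", with a YES/NO answer and no space for the measurement.

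**Reference standard.** Section 11.1 plans an ROC analysis of the cone beam CT, with AUC, 95% confidence interval and an optimal cut-point, "Using medial clear space >4mm for the gravity stress X-ray as the gold standard". This is an absolute value on the stress film, with no term for change from rest.

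**Status.** Section 1.1 opens this aim with "An exploratory objective of this study is to determine if sensitivity of the investigational cone beam CT scan can be verified", the gravity stress film being the comparator. The primary objective concerns the same measurements on the two modalities.

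**Data kept.** Section 9.6 lists "data from the gravity stress X-rays and CT scans (medial clear space distance" and further distances. Attachment D has one radiograph form, headed "SER Ankle Fracture Instability STUDY: X-RAY DATA COLLECTION FORM", with one medial clear space field.

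**The concern.** The 4 to 5 mm band is below the entry limit and above the reference limit. An ankle can sit in it at rest, stay there under stress, and count as positive without having widened. Section 2.1 describes instability in terms of widening, so a reader may expect the reference to register a response to stress.

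If many patients were in that band, the AUC and the CT cut-point could partly reflect how wide the ankle was before any load. A CT that reproduced resting width and nothing more could then score better than chance. Because the resting distance is recorded only as meeting the entry limit or not, the planned dataset would not show how many positives were of this kind. At stake is the reading of one exploratory result.

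**Working it through.** **The plan's own figure.** The only computed figure is the power in section 11.2: n = 20, SD of the paired difference 1.5 mm, difference 1 mm, alpha 0.05 (taken as two-sided). The noncentrality is 1/(1.5/√20) = 2.98 on 19 degrees of freedom, giving power 80.7% against the stated 80%. It concerns the paired t-test, which uses neither the 4 mm nor the 5 mm limit, so nothing here bears on it.

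**The two limits side by side.** Rest 4.5 mm is below 5, so eligible. Stress 4.5 mm is above 4, so positive. The overlap is real. But the label is the stress reading itself: rest 4.5 mm with stress 3.9 mm is negative. Resting width makes a positive label likelier; it does not fix it.

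**How many ankles.** The documents give no distribution of resting width. Assume X normal, truncated at 5 mm, with mean 3.0 to 4.0 mm and SD 0.5 to 1.0 mm. The share above 4 mm is [Φ((5−μ)/σ) − Φ((4−μ)/σ)] / Φ((5−μ)/σ). Multiplying by 20 gives the expected number of patients.

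**Effect on the AUC.** All further inputs are also assumed:
- half the ankles widen by w = max(N(1.5, 0.7), 0) mm, the rest by 0, independently of X;
- stress film = X + w + N(0, 0.3);
- CT = X + k·w + N(0, 0.7), where k is the share of the widening that the CT shows;
- positive means stress film > 4 mm.

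The table gives the AUC in all ankles → the AUC after dropping those with X > 4 mm, from 1 million draws per cell.

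| Mean / SD (mm) | Share above 4 mm | Of 20 | k = 1 | k = 0.5 | k = 0 |
|---|---|---|---|---|---|
| 3.0 / 0.5 | 0.023 | 0.45 | 0.909 → 0.910 | 0.803 → 0.798 | 0.593 → 0.579 |
| 3.0 / 1.0 | 0.139 | 2.8 | 0.922 → 0.918 | 0.865 → 0.836 | 0.747 → 0.675 |
| 3.5 / 0.5 | 0.158 | 3.2 | 0.884 → 0.888 | 0.794 → 0.777 | 0.617 → 0.563 |
| 3.5 / 1.0 | 0.259 | 5.2 | 0.911 → 0.906 | 0.858 → 0.816 | 0.748 → 0.643 |
| 4.0 / 0.5 | 0.488 | 9.8 | 0.855 → 0.860 | 0.792 → 0.754 | 0.659 → 0.547 |
| 4.0 / 1.0 | 0.406 | 8.1 | 0.901 → 0.895 | 0.854 → 0.800 | 0.753 → 0.617 |

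From the table, the change is −0.006 to +0.005 at k = 1. The fall is 0.005 to 0.054 at k = 0.5 and 0.014 to 0.136 at k = 0. In this model 14% to 29% of non-widening ankles resting above 4 mm are reference-negative, because of stress-film error alone.

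**What an added analysis would show at n = 20.** In simulated trials of 20 patients (4,000 per cell), the fall at k = 0 averages 0.013 to 0.136 with SD 0.034 to 0.142. The chance that a trial with k = 0 shows a larger fall than one with k = 0.5 is about 0.54 to 0.72, where 0.5 is a coin toss. At mean 3.0 and SD 0.5, about 71% of k = 0 trials show no fall. Exclusion does not remove the resting-width contribution either: the k = 0 AUC stays at 0.55 to 0.67.

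**The case for a change.** The best case for acting is that it would cost almost nothing. The standard film is already read at screening. One extra field and one table of counts would tell readers how many positives were above 4 mm before stress, and a table needs no power. Without them, a CT that shows none of the widening gives a planned AUC of 0.59 to 0.75 in this model, although its AUC for the simulated instability is 0.50.

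Part of this stands. The overlap exists, the resting distance is not a planned study variable, and the table would be informative.

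The rest is weaker. The 0.50 is built in: the model makes instability independent of resting width and sets the CT response to zero, and nothing in the documents supports either choice. Section 2.1 accepts widening on standard films as a sign of deltoid rupture, so a patient resting above 4 mm is not shown to be mislabelled. No objective concerns change from rest. An AUC that isolates response to stress would answer a question that the protocol does not ask.

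The gap in the data is also narrower than it looks. Section 9.5 names medical records as the source for screening and Attachment A has a notes box, so the value is probably recoverable. Nor is it unclear which film the radiograph form describes: section 9.6 ties Attachment D to the gravity stress film, and section 11.4 sends the radiologist only the stress and CT images.

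**Conclusion.** No change to the plan is needed. Entry and reference limits refer to different films and are compatible. The ROC sets one absolute distance against the same absolute distance on the protocol's chosen comparator, which is what the exploratory objective asks for, and no stated rule gives a wrong result.

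The size cannot be derived from the documents. On the assumptions above it runs from nil (AUC change within about 0.006 if the CT shows the full widening) to a fall of about 0.14 in a hypothetical worst case where it shows none. A repeat ROC in 20 patients could not reliably tell those situations apart, and it would rest on an unblinded clinical reading rather than the blinded, repeated measurements of section 11.4.

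Analysts who want the context can take the screening value from the record and tabulate resting width (4 mm or less, above 4 mm) by reference status. That is an optional description beside an analysis that stays as written.
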